8.3 Final Analyses and Reporting

An initial data freeze will occur once all subjects have completed the treatment period and all subject data through Visit 5/EOT has been monitored. Analysis populations will be identified and the Project Statistician will be unblinded in order to produce key summary tables that will be provided to the Sponsor. Final database lock will occur after all subjects have completed the study assessment period (or discontinued early) and all subject data has been monitored. The EOS visit captures safety (AE and LSR) data only.

Further exploratory analyses not necessarily identified in this SAP may be performed to support the clinical development program. Any post-hoc or unplanned analyses performed and not described in this SAP will be clearly identified in the CSR.

8.4 Sample Size

No formal sample size calculations were performed for this study given it is an initial proof of concept study.

8.5 Randomization and Blinding

Subject randomization will be stratified by sex and age (18-25 years old / 26-40 years old). Subjects will be randomized at a 2:1 ratio to NB01 (10^5 CFU/cm²) or Vehicle which are to be applied at approximately the same time each evening for 11 weeks.

8.6 Subject Disposition

The number and percent of subjects who were enrolled in the study, in each analysis population, who completed the study, who withdrew from the study and their reasons for discontinuation will be tabulated by treatment group.

Protocol deviations will be provided in a listing and summarized by deviation type by treatment group and overall for the mITT population. Subjects who are excluded from the PP population will be identified in this listing.

Subjects who are screen failures with their reason for screen failure will be provided in a listing. The frequency distribution of the reasons for screen failure will be tabulated.

8.7 Screening and Baseline Assessments

8.7.1 *Demographics*

Demographic and baseline characteristics including age, sex, ethnicity, and race will be summarized by treatment group for the mITT, PP and Safety populations. Demographic data for screen failures will be summarized separately.

If a subject has more than one self-reported race, then he/she will be summarized in “multiple” category.

8.7.2 *Medical History*

Medical history will be presented in a subject listing.

8.7.3 *Physical Examination*

Abnormal findings noted during the Screening and Baseline examinations will be captured in the Medical History and not presented separately.

8.7.4 Vital Signs

Descriptive statistics will be provided by treatment group and overall for systolic and diastolic blood pressure, heart rate, and temperature for the Safety population.

8.7.5 Baseline Clinical Evaluations

Screening and Baseline IGA scores will be tabulated and descriptive statistics will be for the acne lesion counts, QoL domain scores, sebum production, and the skin surface engraftment parameter Cas5/PanBac ratio will be provided by treatment group and overall for the mITT and PP populations. Results of the follicular engraftment sample at Screening will also be presented as the proportion of subjects with live NB01 by treatment group and overall.

8.7.6 Baseline Local Skin Reactions

Frequency distributions of the Screening and Baseline local skin reaction severity scores will be presented by treatment group and overall for the Safety population.

8.8 Dosing Compliance

Subjects who consent to participate in the study are to apply 5% topical BPO gel QD for 5 to 7 days prior to randomization at the Baseline visit (Day 1). The number of days of BPO dosing and the number of doses applied during the screening period will be tabulated by treatment group and overall for the mITT and PP populations. The proportion of subjects compliant with BPO dosing will also be tabulated where compliance is defined as at least 5 days of BPO application during the week prior to Day 1 with the last BPO application occurring 24-48 hours prior to Day 1 and no BPO application within approximately 24 hours of the Day 1 visit.

Descriptive statistics will be used to summarize for each treatment group the duration (days) of treatment (defined as last dose date – first dose date +1), the total number of applications (determined from the doses reported in the Subject Diary), and the percent of expected doses applied for the mITT and PP populations. The protocol specifies that a subject will dose each evening for 11 weeks for a total of 77 doses. Visit 5/EOT is expected to occur 3 to 7 days after the last dose is applied, therefore, the final dose should be applied between Study Days 73 to 77, inclusive. Accordingly, the percent of expected doses applied by a subject will use 75 doses as the denominator. Subjects who apply at least 80% of the expected total number of applications and have no other evidence of material dosing non-compliance will be considered to be compliant with study drug dosing.

8.9 Exploratory Engraftment Evaluation

The engraftment analyses will be conducted on the mITT and PP populations.

8.9.1 Skin Engraftment

For the endpoint of skin engraftment, the change and percent change in Cas5/PanBac, deoR/PanBac, and Transposase2/PanBac ratio from Screening at each follow-up visit, will be summarized with descriptive statistics at each visit. NB01 and VEH will be compared at Visit 5/EOT with respect to change or percent change values using Mixed effect Model Repeated Measures (MMRM).

The MMRM model used for the analysis of continuous variables will include treatment, visit, treatment by visit, and investigator site as fixed effects, the Screening value as a covariate, and subject as a random effect. The MMRM analyses will be based on observed data. The p-value for the hypothesis of no treatment difference at Visit 5/EOT will be reported. The MMRM analysis will use an unstructured covariance type. The Kenward-Roger method will be used to estimate denominator degrees of freedom.

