5. STUDY DRUG PRODUCT

5.1. Randomization, Blinding and Treatment Codes

5.1.1. Procedure for Subject Randomization

Subjects will be randomized to one of the two Treatment Groups on a 2:1 basis (NB01 or vehicle-control) using a central randomization scheme. Randomization will be stratified by sex (male/female) and age (18-25 years old/26-40 years old).

Subjects will be randomized on Day 1 after the subject has arrived at the site and eligibility has been confirmed. To randomize a subject the PI or designee will call the contract research organization (CRO) and provide the required subject information. The CRO will have a designated unblinded staff member available to assign a study drug kit number to the subject, which contains the treatment specified by the randomization schedule. A subject randomization form documenting study drug kit number assignment will be provided to the site by the CRO.

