8.4.3. Exploratory Engraftment Analyses

The engraftment analyses will be conducted on the ITT and PP populations.

Engraftment Assay

For endpoint of Engraftment Assay of Cas5/PanBac, the absolute and percent change from Screening at each follow-up visit, the comparison between NB01 and vehicle-control will be analyzed using ANCOVA model with the dependent variable being absolute or percent change values and the factor treatment and the Screening value as a covariate in the model, with and without LOCF imputation.

For endpoint of Follicular Biore®, the treatment groups will be compared with respect to the proportions of subjects with “success” at Week 12 using the CMH test with and without stratification on study center, where “success” is defined as a Follicular Biore® with “yes” outcome based on the recovery of live NB01.

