8.9.2 Follicular Engraftment

Multiple samples were obtained at Screening and Visit 5/EOT visits for a subject. The mean of each parameter, Cas5/PanBac, deoR/PanBac, and Transposase2/PanBac ratio, will be determined for each visit and serve as the observation for that visit. The change and percent change in Cas5/PanBac, deoR/PanBac, and Transposase2/PanBac ratio from Screening at Visit 5/EOT will be summarized with descriptive statistics. NB01 and VEH will be compared at Visit 5/EOT using MMRM.

The treatment groups will also be compared with respect to the proportions of subjects with “success” at Visit 5/EOT using the Cochran-Mantel-Haenszel (CMH) test with and without stratification on study center, where “success” is defined as a Follicular Biore® with “yes” outcome based on the recovery of live NB01. If any one of the samples at a given visit has live NB01, the success outcome is “yes” for that visit.

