8.10 Exploratory Sebum Evaluation

8.10.1 Sebum Production

For the endpoint of sebum production, the observed, change and percent change from Screening values at each follow-up visit will be summarized with descriptive statistics. NB01 and VEH will be compared at Visit 5/EOT using MMRM.

Sebum production data will not be available for all subjects. One site, [name] (Site 4), did not have a Sebumeter, therefore, sebum production was not assessed for any subject. Site 3, [name], received a Sebumeter after having started enrollment of subjects. Some of the site’s subjects will not have any sebum data while others may have only partial data with the Screening values missing. Subjects without any sebum data will be excluded from the summaries and analyses. Subjects with partial data will be included in the summaries for observed values where data is

available, but will be excluded from summaries and analyses for change and percent change from Screening.

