8.11.1 Investigator's Global Assessment

The observed and change from Screening scores at each follow-up visit will be tabulated. For the endpoint of IGA, the treatment groups will be compared with respect to the proportions of subjects with (a) at least one-point improvement and (b) at least two-point improvement in IGA score relative to Screening at each follow-up visit using the CMH test with and without stratification on study center.

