8.11.4.5 Examination of Subgroups

Subgroup analysis for IGA, lesion counts, and sebum production will be performed based on the following subgroups at Visit 5/EOT only:

- Sex: male | female
- Age: 18-25 years | 26-40 years
- Follicular engraftment success: yes | no

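### The MMRM omits sex and age group, the factors that stratify randomisation, so its exploratory tests are conservative and lose some power if those factors predict outcome

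*SAP*

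**What the plan says.** Protocol 5.1.1 sets the allocation: "Randomization will be stratified by sex (male/female) and age (18-25 years old/26-40 years old"). SAP 8.5 repeats it: "Subject randomization will be stratified by sex and age (18-25 years old / 26-40 years old"). Allocation is 2:1 and 36 subjects were randomised (Protocol 3.3), so about 24 receive NB01 and 12 vehicle. Centre is not a stratification factor.

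SAP 8.9.1 defines the MMRM for continuous variables with these terms: "treatment, visit, treatment by visit, and investigator site as fixed effects, the Screening value as a covariate, and subject as a random effect". The same method serves the follicular gene ratios (8.9.2), sebum (8.10.1), lesion counts (8.11.2) and Acne-QoL (8.11.3). Neither sex nor age group is in it.

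The binary endpoints are compared "using the Cochran-Mantel-Haenszel (CMH) test with and without stratification on study center" (follicular success, 8.9.2) and, for IGA, "using the CMH test with and without stratification on study center" (8.11.1).

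Sex and age group enter the comparative analyses in one place, SAP 8.11.4.5: "Subgroup analysis for IGA, lesion counts, and sebum production will be performed based on the following subgroups at Visit 5/EOT only". The plan gives no reason for leaving them out of the model.

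**The concern.** The model adjusts for site, which was not used in the randomisation, and not for the two factors that were. When arms are balanced within strata, a prognostic stratification factor makes the treatment estimate vary less from trial to trial. A model without that factor does not see the reduction, because the factor's variance stays in the residual. The reported standard error is then larger than the true one.

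The subgroup analyses do not repair this. They split the data by sex and by age group and leave the main comparison unadjusted.

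At stake is precision that the design has already bought. With about 24 against 12 subjects and no sample size calculation (SAP 8.4), a proof-of-concept study has little precision to give away.

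**Working it through.** The documents state no power, effect size, SD or significance level, so there is no figure of the plan's to reproduce. The check asks which way the error runs and how large it could be.

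**Inputs from the documents.** 36 subjects, 2:1, four sex-by-age strata, three centres, three post-baseline clinic visits, and the MMRM terms above.

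**Assumed inputs.** Two-sided 5% level; treatment effect of 0.9 SD at Visit 5; post-Screening SD of 1; permuted blocks of three; strata of equal expected size; subjects spread at random over centres; visit correlations of 0.6 (adjacent) and 0.48; complete data. R² is the share of post-Screening variance explained by sex and age together, varied from 0 to 30%.

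**Step 1: the mechanism.** With SD 1, the standard error of a 24 v 12 difference is √(1/24 + 1/12) = 0.354. Under perfect within-stratum balance the true value falls to 0.354 × √(1 − R²), while the model without the strata still estimates about 0.354. Simulating the MMRM (10,000 trials per scenario, prognostic effect equal at all visits) gives:

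| R² | Mean model SE | Actual SD of estimate | Ratio | 2[1 − Φ(1.96 × ratio)] | Simulated type I error |
|---|---|---|---|---|---|
| 10% | 0.363 | 0.353 | 1.028 | 4.4% | 4.2% |
| 20% | 0.365 | 0.334 | 1.093 | 3.2% | 3.3% |
| 30% | 0.366 | 0.319 | 1.147 | 2.5% | 2.3% |

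The overstated standard error accounts for the conservatism.

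**Step 2: power.** Entries are the SAP model's type I error, then the change in power (percentage points) from adding sex and age group as main effects. The ANCOVA is a separate single-visit simulation with the same effect size.

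| R² | MMRM, equal effect at all visits | MMRM, effect growing over visits (1/3, 2/3, full) | Single-visit ANCOVA |
|---|---|---|---|
| 0% | 5.0%, -0.5 | 4.8%, -0.7 | 4.9%, -0.4 |
| 5% | 4.8%, +1.7 | 4.9%, +1.2 | not run |
| 10% | 4.2%, +3.1 | 4.1%, +3.3 | 4.3%, about +4 |
| 20% | 3.3%, +8.0 | 3.1%, +6.2 | 3.2%, about +8 |
| 30% | 2.3%, +12.5 | 2.2%, +10.4 | 2.4%, about +12 |

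In the equal-effect runs, power before adjustment is 66 to 68%. The adjusted MMRM has type I error of 4.5 to 5.4%. The follicular ratios have one scheduled post-Screening visit, so the ANCOVA column represents them better.

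**Step 3: sebum.** SAP 8.10.1 says one site "did not have a Sebumeter, therefore, sebum production was not assessed for any subject", and another has partial data. The size of the subset is not given; 20 subjects is assumed. Adding the two factors changes power by -1.6, -0.2, +2.0, +5.5 and +12.2 points at R² of 0, 5, 10, 20 and 30%, from 38 to 40%. The single-visit ANCOVA puts the cost at R² = 0 at about 2 points.

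**Step 4: CMH.** For an IGA-type endpoint (assumed 20% v 60%), power with stratification by centre against sex by age is:

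| Odds ratio of sex and of age | No centre effect | Centre shifts ±0.8 log-odds | Centre shifts ±1.2 log-odds |
|---|---|---|---|
| 1.0 | 61.1 v 63.1% | 65.3 v 63.8% | 70.4 v 65.0% |
| 1.8 | 62.1 v 66.1% | 66.2 v 65.8% | 69.5 v 65.2% |
| 2.7 | 62.2 v 67.9% | 66.7 v 69.1% | 69.5 v 67.7% |
| 5.0 | 62.8 v 73.8% | 64.7 v 71.6% | 68.2 v 71.9% |

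Neither stratification wins throughout. For follicular success at an assumed 5% v 40%, unstratified against sex by age gives 68.0 v 66.4%, 68.1 v 67.5%, 67.9 v 69.4% and 67.8 v 73.2% at the same odds ratios. The gain is small or absent unless the factors are strong.

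**The case against.** The strongest reply is that the benefit is assumed. Nothing in the documents shows that sex or age predicts any outcome beyond the Screening value. Entry criteria also narrow the population: IGA exactly 3, bounded lesion counts, age 18 to 40, and non-cyclical acne in women. For bacterial gene ratios there is no stated reason to expect a sex or age effect. At R² of 0 to 10% the MMRM change is only -0.7 to +3.3 points. All of this stands and limits the size of the point. It does not reverse it, because adjustment costs under 1 point at n = 36 if the factors turn out to be irrelevant.

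The simulations also assume complete data and a random sebum subset. Randomisation is not stratified by site, so within-stratum balance is not assured in a subset defined by site. This too stands, and is why sebum is treated separately below.

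Three stronger readings are tempting, and the documents support none of them.

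- A reader might infer that the CMH tests are defective in the same way. They also omit sex and age group, but step 4 shows that the better stratification depends on centre effects that nobody knows yet. An extra version has a cost too: IGA already yields 2 thresholds × 3 visits × 2 populations × 2 versions = 24 p-values; a third version makes 36, and SAP 8.11.4.4 plans no multiplicity adjustment.
- A reader might infer an undeclared departure from the protocol. The protocol's own ANCOVA has only "the factor treatment and the Screening value as a covariate in the model" and its CMH tests name only study centre, so SAP section 9 owes no entry for this.
- A reader might infer that the planned tests are invalid. Under stratified balance the error runs only in the conservative direction.

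**Conclusion.** The point holds for the MMRM. The omission is certain, and its direction follows from the design; its size is conditional. Under the stated assumptions, adding sex and age group to the full-sample MMRM changes power by about -0.5 points if they explain nothing, +3 to +4 points at 10% and +6 to +8 points at 20% of post-Screening variance. The larger gains at 30% need a prognostic strength for which the documents give no support. Every affected test is exploratory, false positives are not inflated, and the primary safety summaries do not use the model. This is a worthwhile efficiency correction of modest weight. For the CMH tests no defect is shown.

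**What to change.** 1. In SAP 8.9.1, add sex and age group (18-25 / 26-40) as main-effect fixed effects to the MMRM. Do this before the data freeze at which the project statistician is unblinded (SAP 8.3); made later, the adjustment would be post hoc.
2. For sebum (SAP 8.10.1), keep the current model as the main analysis and report the adjusted model as a sensitivity analysis.
3. Leave the CMH tests in SAP 8.9.2 and 8.11.1 as planned. If a version stratified by sex and age group is wanted, label it a sensitivity analysis and do not give it equal standing. Do not cross these strata with centre, since 4 × 3 = 12 cells for 36 subjects average three each.

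The cost is a change of SAP wording and two model terms; both variables are already defined for the subgroup analyses. The statistical price is two degrees of freedom: under 1 power point at n = 36, and about 2 points in an assumed sebum subset of 20, if the factors are not prognostic.

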6.2.2. Baseline Assessments – Visit 2 (Day 1)

The following will be performed and documented at the Day 1 visit:

- Reconfirm inclusion/exclusion criteria and subject eligibility.
- Review of Screening Subject Diary.
- Limited physical examination.
- Vital signs.
- UPT.
- Sebum levels, measured at the mid-glabellar region of the forehead using a Sebumeter SM – 815 (COURAGE + KHAZAKA electronic GmbH, Köln, Germany).
- Assess AEs.
- Assess LSRs.
- Review concomitant medications, topical facial products and procedures/therapies.
- IGA.
- Acne Lesion Counts (total, inflammatory, and non-inflammatory lesion counts).
- Quality of life assessment (Acne QoL Questionnaire).
- Optional facial photography.
- Cheek swab skin engraftment sample.
- Randomize the subject (see [Section 5.1.1](#)).
- PI or designee shall apply the first dose of study drug and review application instructions with the subject.

- Dispense Subject Diary (for documentation of at-home Cetaphil® BID washes and evening study drug application).
- Dispense Study Drug and gloves, reminding the subject that study drug is to be stored in the freezer
- Schedule the next visit.

6.2.3. Treatment Assessments - Visit 3 (Week 2/Day 8), Visit 4 (Week 7/Day 43) and Visit 5 (Week 12/End of Treatment/Day 80)

The following will be performed and documented at each visit during the treatment phase:

- Collect, review, and dispense Subject Diary. NOTE: In review of the Subject Diary, the PI should question the subject to gauge understanding of application instructions, and re-instruct, at each visit except Visit 5, EOS.
- Sebum levels, measured at the mid-glabellar region of the forehead using a Sebumeter SM – 815 (COURAGE + KHAZAKA electronic GmbH, Köln, Germany).
- Assess AEs.
- Assess LSRs.
- Review concomitant medications, topical facial products and procedures/therapies.
- Limited physical examination (**Visit 5/EOT only**).
- Vital signs (**Visit 5/EOT only**).
- UPT (**Visit 5/EOT only**).
- Local CBC (**Visit 5/EOT only**).
- IGA.
- Acne Lesion Counts (total, inflammatory, and non-inflammatory lesion counts).
- Quality of life assessment (Acne QoL Questionnaire).
- Optional facial photography.
- Cheek swab skin engraftment sample.
- Face wash with Cetaphil® (**only at Visit 5/EOT prior to Biore® strip sampling**).
- Biore® strip follicular engraftment sample (**Visit 5/EOT only**).
- Dispense Study Drug (**only at Visit 3 and Visit 4**).
- Schedule the next visit.

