8.4.4. Exploratory Efficacy Analyses

The efficacy analyses will be conducted on the ITT and PP populations.

Investigator’s Global Assessment

The observed and change from Screening scores at each follow-up visit will be tabulated. For endpoint of IGA, the treatment groups will be compared with respect to the proportions of subjects with (a) at least a one-point improvement and (b) at least a two-point improvement in IGA score relative to Screening at each follow-up visit using the CMH test with and without stratification on study center.

Acne Lesion Counts

For endpoint of Acne Lesion Counts, the absolute and percent change from Screening at each follow-up visit in total, inflammatory, and non-inflammatory lesions, the comparison between NB01 and vehicle-control will be analyzed using Analysis of Covariance (ANCOVA) model with the factor treatment and the Screening counts as a covariate in the model, with and without Last Observation Carried Forward (LOCF) imputation.

Acne Quality of Life

For endpoint of Acne-QoL, the absolute and percent change from Screening at each follow-up visit on four domains separately and total, the comparison between NB01 and vehicle-control will be analyzed using ANCOVA model with the factor treatment and the Screening score as a covariate in the model, with and without LOCF imputation.

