8.11.2 Acne Lesion Counts

For the endpoint of Acne Lesion Counts, the change and percent change from Screening at each follow-up visit in total, inflammatory and non-inflammatory lesions, NB01 and VEH will be compared at Visit 5/EOT using MMRM. Descriptive statistics will be provided for the observed and the change and percent change from Screening at each visit.

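### The MMRM fits one Screening slope for all visits; adding Screening-by-visit would be a cheap, optional gain in precision at Visit 5

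*SAP*

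**What the plan says.** SAP 8.9.1 sets out a single model for every continuous endpoint. Its terms are given as "treatment, visit, treatment by visit, and investigator site as fixed effects, the Screening value as a covariate". A random subject effect is listed as well. The section adds that "The MMRM analysis will use an unstructured covariance type" and that "The p-value for the hypothesis of no treatment difference at Visit 5/EOT will be reported". The sections on sebum (8.10.1), lesion counts (8.11.2) and Acne-QoL (8.11.3) refer back to it without adding terms; for lesion counts, "NB01 and VEH will be compared at Visit 5/EOT using MMRM". None of them includes a Screening-by-visit interaction.

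Protocol 8.4.3 to 8.5 planned ANCOVA on the change at each follow-up visit. For lesion counts (8.4.4) this was a "model with the factor treatment and the Screening counts as a covariate in the model". Fitted visit by visit, it gives each visit its own Screening slope. SAP section 9 explains the move to MMRM only by a preference over LOCF, and does not mention the covariate slope.

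The treatment-period visits in Protocol 6.2.3 are "Visit 3 (Week 2/Day 8), Visit 4 (Week 7/Day 43) and Visit 5 (Week 12/End of Treatment/Day 80").

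**The concern.** For a change score, the Screening slope at a visit is (correlation with Screening x SD ratio) - 1. If the correlation weakens over time, the slope becomes steeper from Day 8 to Day 80. A model with one slope has to compromise, and generalised least squares gives most weight to the visits with the least residual variance. Those are usually the early ones. The Visit 5 contrast is then adjusted with a slope that is too shallow for Visit 5.

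With 24:12 allocation, and stratification by sex and age only, some chance imbalance in Screening severity is to be expected. Part of it would remain in the Visit 5 estimate and widen its standard error. SAP section 9 gives no sign that this was intended.

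**Working it through.** The documents give no power, SD or correlation, so there is no plan figure to reproduce.

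**Inputs from the documents:** 36 subjects at 2:1, taken as 24:12 (Protocol 3.3); three follow-up visits; unstructured covariance; Visit 5 as the tested contrast.

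**Assumptions:** correlations and SDs as listed in the table, with Screening SD = 1; normal outcomes; complete data; Day 1 (pre-dose) not used as a response. The calculation is for change, not percent change.

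**Formulas (large sample)**
- Visit slope: beta_j = r_j x SD_j - 1.
- Common slope: b = sum of w_j x beta_j, with w proportional to S^-1 x 1, where S is the residual covariance given Screening.
- Visit 5 variance ratio, common slope to visit-specific slope: 1 + (b - beta_5)^2 x var(Screening) / residual variance at Visit 5.

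**Worked case: correlations 0.8/0.6/0.4, equal SDs.** Assume follow-up correlations of 0.75 (Visits 3-4), 0.55 (3-5) and 0.70 (4-5).
- Residual variances: 1 - 0.64 = 0.36; 1 - 0.36 = 0.64; 1 - 0.16 = 0.84.
- Residual covariances: 0.75 - 0.48 = 0.27; 0.55 - 0.32 = 0.23; 0.70 - 0.24 = 0.46.
- Weights: 0.765/0.105/0.130. Check: each row of S times these weights gives about 0.334.
- b = 0.765(-0.2) + 0.105(-0.4) + 0.130(-0.6) = -0.273, against beta_5 = -0.60.
- Ratio: 1 + 0.327^2/0.84 = 1 + 0.107/0.84 = 1.127.

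**Range.** The last column comes from simulated 24:12 trials with an unstructured fit, 800 to 3,000 per scenario.

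| Screening correlation with Visits 3/4/5 | Visit slopes | Common slope | Visit 3 weight | Large-sample ratio | Simulated ratio, N=36 |
|---|---|---|---|---|---|
| Flat 0.6/0.6/0.6 | -0.40 at each | -0.40 | 33% | 1.00 | 0.98-0.99 |
| Mild 0.7/0.6/0.5 | -0.30/-0.40/-0.50 | -0.368 | 53% | 1.02 | 1.00-1.02 |
| AR(1) 0.80/0.64/0.51 | -0.20/-0.36/-0.49 | -0.259 | 78% | 1.07 | 1.04-1.09 |
| Moderate 0.8/0.6/0.4 | -0.20/-0.40/-0.60 | -0.273 | 76% | 1.13 | 1.08-1.11 |
| Moderate, SD growing to 1.4 | -0.20/-0.28/-0.44 | -0.206 | 94% | 1.03 | 1.00-1.01 |
| Moderate, SD shrinking to 0.7 | -0.28/-0.52/-0.72 | -0.438 | 59% | 1.19 | 1.12 |
| Steep 0.9/0.6/0.3 | -0.10/-0.40/-0.70 | -0.143 | 93% | 1.34 | 1.25-1.29 |

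Correlations among the follow-up visits also matter. Under other assumptions about them, the moderate pattern gives about 1.15, and the shrinking-SD pattern up to about 1.2.

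**Effect of the eligibility limits.** Screening inflammatory counts must lie in 20-50 and non-inflammatory counts in 20-125 (Protocol 4.2). Under a linear model, selection on Screening leaves slopes and residual variances unchanged but reduces var(Screening), and so the penalty. If the limits act like truncation at +/-1.2 SD (an assumption), var(Screening) falls to 1 - 2.4 x 0.1942/0.7699 = 0.395. The excess then falls as follows:
- Mild: 2.3% x 0.395 = 0.9%.
- AR(1): 7.1% x 0.395 = 2.8%.
- Moderate: 12.7% x 0.395 = 5.0%.

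Simulated ratios with truncation were about 1.00-1.05.

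**Imbalance left in the estimate, without truncation.** The SD of the Screening mean difference is sqrt(1/24 + 1/12) = 0.354 SD. The shift left at Visit 5 for an imbalance of that size is |b - beta_5| x 0.354:
- Mild: 0.132 x 0.354 = 0.05 SD.
- Moderate: 0.327 x 0.354 = 0.12 SD.
- Steep: 0.557 x 0.354 = 0.20 SD.

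**Bias.** Randomisation makes the expected imbalance zero, so these shifts average out; simulated null means were within 0.02 SD of zero for both models. In the moderate case the mean model standard error under the common slope (0.344) matched the empirical SD of the estimates (0.346).

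**The case against.** The strongest reply is that a single Screening covariate is a valid, prespecified MMRM, and that any loss comes from assumed correlations. That is right as far as it goes: with flat correlations the interaction gives no gain and a very small cost, and with mild decay or growing SDs it gives almost nothing.

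The design also weakens the premise that early visits track Screening closely. Screening precedes the BPO course and may be up to 14 days before Day 1 (28 in the SAP's analysis window). Day 8 is therefore roughly one to three weeks after Screening, with BPO in between. Even at a correlation of 0.8, the Day 8 slope is -0.2, not zero. For lesion counts, truncation at eligibility reduces the penalty further.

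A reader might draw three stronger conclusions that the documents do not support:
- **That the Visit 5 test is biased or its type I error inflated.** Randomisation protects both; only precision and conditional adjustment are affected.
- **That the SAP model is certainly less efficient than the protocol's ANCOVA.** This depends on unstated correlations. The two analyses also differ in other ways: the ANCOVA had no site term and was to be run with and without LOCF, while the MMRM was chosen to handle missing data.
- **That every endpoint using this MMRM is affected.** Follicular ratios are sampled only at Screening and Visit 5 (SAP 6.4). With one follow-up time point there is only one slope to fit.

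What survives is narrower. Only Visit 5 is tested, so nothing is gained by letting earlier visits set its slope, and the term that prevents this is nearly free.

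**Conclusion.** The point holds as a conditional, modest loss of precision. If the Screening correlation weakens across Days 8, 43 and 80, the SAP model under-adjusts the Visit 5 comparison for chance Screening imbalance. At 24:12 the Visit 5 variance is about 0-10% larger under flat to moderate decay. At 10%, the standard error is about 5% wider (sqrt(1.10) = 1.049), which is like having 36/1.10 = 32.7 subjects instead of 36. For lesion counts under the eligibility limits, about 0-5% is more realistic. Steep decay or shrinking SDs would give more.

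These figures assume complete data, normal outcomes and change scores. Percent change and Kenward-Roger degrees of freedom were not evaluated. The affected endpoints are exploratory, with no sample-size basis and no multiplicity control, and the primary safety objective does not use this model. This is a cheap improvement of optional severity.

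**What to change.** In SAP 8.9.1, add Screening value-by-visit to the fixed effects. State that it applies to the endpoints with several follow-up visits: lesion counts, Acne-QoL, skin engraftment ratios and sebum. For follicular ratios (8.9.2), say that the model has a single post-Screening time point and needs no such term.

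The cost is one line of text and two extra fixed-effect parameters with three follow-up visits. If the slopes are truly equal, the variance cost is about 1-2% at 36 subjects. Sebum has fewer contributing subjects (none at Site 04, only some at Site 03), so the cost there may be somewhat larger. No new data are needed, and the change restores the visit-specific adjustment of the protocol's ANCOVA.
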